	
MODIFY studies with bezlotoxumab vs. placebo (Zinplava Package insert).
 
Those patients meeting the study inclusion/exclusion criteria will be offered open-label Bezlotoxumab infusion. This active intervention arm will have baseline stool samples collected for C difficile culture and typing at study entry and upon CDI relapse, if any
 
The comparator groups will be
 
 1. The historical control group from the Wong study, and 2. A concurrent observational arm – consisting of those patients otherwise eligible for the study, but : 
 A. Not consenting to study enrolment, and B. Taking no form of CDI prophylaxis (no oral vancomycin, metronidazole or fidaxomicin use as defined below). 
All cohort members will be subject to standardized chart review for baseline parameters at study entry, and structured followup by chart review every 2 weeks for 8 weeks for CDI relapse (the primary endpoint), tolerability of study drug (if administered) , length of hospitalization/ICU stay or death.
 
Use of CDI prophylaxis will be adjudicated to see if it conforms to the standards established in the Wong study – prophylaxis used for at least 50% of the duration of the concomitant antibiotics course and at least up to 72 hrs before the end of the concomitant antibiotics. Patients receiving any such prophylaxis will be excluded from the per-protocol analysis, which will be the primary analysis. Secondary analysis will also be performed on an intent-to-treat basis, where group assignment is determined based on use of prophylaxis at study entry only.
 
This design was chosen to parallel that of the retrospective Wong study at our same site – to allow comparisons with the historical treatment groups in that study.

2.4 Study Flowchart
	<pre> graph TD Cdiff_dx[14-90 days Cdiff dx] --> Inpatient Inpatient --> On_Abx{On Abx?} On_Abx -- No --> Follow_daily[Follow daily] On_Abx -- Yes --> On_CDI_ppx{On CDI ppx?} On_CDI_ppx -- Yes --> Offer_Bezlo[Offer Bezlo Study] Offer_Bezlo --> Enrol[Enrol] Offer_Bezlo --> Cdiff_Cx[C diff Cx and f/u 8 wks] On_CDI_ppx -- No --> Decline[Decline] Decline --> Follow_8_wk[Follow for 8 wk] Follow_8_wk --> Relapse_no_ppx[Relapse, no ppx No Relapse, no ppx] Follow_8_wk --> Relapse_Bezlo[Relapse, Bezlo No Relapse, Bezlo] </pre>

2.5 Study
	
STUDY DESIGN

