-------------------	--

	
overlap with extended initial CDI treatment regimens, AND.
 
3. Encompassing all antibiotics separated by up to 72 hrs linked into the same course, AND4. Ending with the first episode of CDI relapse, as all concurrent (started within 48HR of recurring C. difficile symptoms) and subsequent antibiotic courses are excluded from further analysis 
A course with CDI prophylaxis is defined as:
 
1. Having concurrent use of either metronidazole (intravenous or oral) or oral vancomycin or fidaxomicin therapy for at least 50-percent of the duration of the high risk antibiotic course, AND2. Having prophylaxis to within 72 hours of the last dose of the high-risk antibiotic agent; thus an extended high risk antibiotic course may have a segment covered by prophylaxis, but if the last 3 days are no longer receiving the potential benefit of prophylaxis, the course is considered to be unprophylaxed. 
A CDI relapse is defined as:
 
1. Attributable to a high risk antibiotic exposure if clinical symptoms and/or positive stool assay developed greater than 48-hours after antibiotic exposure, AND2. Occurring within 8 weeks of completion of the high risk antibiotic course, AND3. Compatible with clinical evidence suggestive of CDI disease during chart review; including a leukocytosis without alternative etiology and responding to CDI treatment, new onset of diarrhea, presence of radiographic or if relevant autopsy evidence of colitis, and/or repeat positive stool assay with appropriate clinical symptoms. If these indicators of CDI were present at the time of antibiotic onset, or within 48hrs, this was deemed a recurrence of infection NOT attributable to the high risk antibiotic course and was omitted from the relapse population. 
The beneficial effects of Bezlotoxumab will be considered to last for the entire 8 week observation period, regardless of the number or timing of antibiotic courses within that period. Analysis of the effects of cumulative exposure to high-risk antibiotics or exposure late in this period will be assessed separately. The effect of subsequent CDI-active antibiotics, while excluded within 24 hrs of Bezlotoxumab dosing but potentially used within the Bezlotoxumab therapeutic window, will also be considered in secondary analyses (intent-to-treat).
 
LABORATORY INVESTIGATION
 
Using a C. difficile toxigenic culture well-established in the laboratory of the PI (referenced in Boyanton, 2012), stool will be collected by rectal swab from consented subjects in the Bezlotoxumab arm. If subsequent stool samples are sent to our clinical microbiology laboratory for any reason, they are routinely held for 5 days and would be available for C difficile toxigenic culture. Isolated organisms can be comparatively typed by the multi-locus variable number tandem repeat methodology (Marsh, 2007) with great variability in the 3 amplified PCR product sizes. Common letters (below) reflect isolates from neighbor pairs (same ward, same week) albeit each column is a unique patient.

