--	---

	 L A A B B C C D D E E F F G G H H H L	
2.6 Study Duration	
Estimate of 1 year required to recruit 50 patients (from an estimated 150 eligible) and another 6 months to complete the study analysis. A computer simulation indicates there should be 150 eligible subjects in 1 year. Of these, ~50 will be on prophylaxis and ~50 will decline participation and will be followed as no prophylaxis controls.
	
2.7 Statistical Analysis and Sample Size Justification	
The PI and local statistician will be responsible for analyzing the study data.
 
Variables/Time Points of Interest
 
The primary outcome variable is relapse of CDI within 8 weeks of study entry. Secondary outcomes are relapse of CDI within 4 weeks of study entry (the interval with highest protective antibody levels), all-cause mortality, time to relapse and duration of hospitalization.
 
Baseline variables collected for each subject include : age, gender, number/dates/treatment of prior CDI episodes, current PPI use and H2-blocker use, Charlson score, immunosuppression, Inflammatory Bowel Disease or Irritable Bowel Syndrome, use of cathartics/lactulose, and indication for current antibiotics.
 
Variables related to the past CDI episode include markers of disease severity : WBC, fever >100.5°F, creatinine, albumin – to generate a Zar score (Zar,2007)
 
Statistical Methods
 
The analysis population is the per-protocol population, with 2 major comparator groups – those receiving Bezlotoxumab and those with no prophylaxis. The latter will be comprised of 3 subgroups – the control group from the Wong study and 2 concurrent observation groups- a PASSIVE followup group of subjects undergoing chart review , and an ACTIVE followup group of subjects declining study drug but agreeing to phone followup at 8 weeks. All groups will be compared across baseline parameters cited above. Risk factors pre-specified for recurrent CDI include age, immunocompromise, and severe CDI will be compared across groups, and tested for associations for the major outcomes of CDI relapse and mortality at 4 weeks and 8 weeks.
 
In the Wong study, there was a remarkably equal distribution of variables among the
	

[figure not shown]

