antibiotic prophylaxis and no prophylaxis groups. We similarly expect no imbalance between our current study and observation groups in terms of risk factor distribution, though self-selection bias will be considered at the interim analysis after 30 intervention patients are enrolled.

Categorical variables will be compared using chi-square and Fisher's Exact analysis and continuous variables will be compared using Mann-Whitney analysis, with $p < 0.05$ considered to be significant.

In survival analysis (Kaplan-Meier), time to CDI relapse is defined from the date of bezlotoxumab study dosing or study refusal - to the date of relapse and limited by a maximum observable window of 8 weeks from the dose of bezlotoxumab. Subjects are censored on the date of death, if death occurred within the observable window, or at the beginning of a new potential antibiotic prophylaxis course (i.e.. If within the 8 week observation period there is receipt of metronidazole, oral vancomycin or fidaxomicin.) or receipt of fecal microbiota transplant. A Cox proportional hazards model will be used for group comparison when adjusting for covariates.

The survival analysis from the Wong study, demonstrating the benefits of antibiotic prophylaxis on preventing relapsed CDI, is summarized in the following figure:

Relapse Free Duration

For the second objective, rates of CDI relapse will be compared among study subjects with or without *C. difficile* colonization at study entry. This is an exploratory study to inform future studies. It is expected that 20% of subjects will be colonized at study entry (based on Sunkesula, 2013) –the expected number of these that relapse is unknown, as data is conflicting on whether colonization is protective or predictive of relapse.

Power/Sample Size:

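### Historical and retrospective-chart controls have no defined day 0 on the primary endpoint's clock, so their relapse window may differ from the bezlotoxumab arm's

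*Combined protocol and SAP*

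**What the plan says.** **Primary endpoint.** Section 2.7 (Variables/Time Points of Interest): "The primary outcome variable is relapse of CDI within 8 weeks of study entry".

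**Time-to-relapse clock.** Section 2.7 (Statistical Methods): "time to CDI relapse is defined from the date of bezlotoxumab study dosing or study refusal", and "limited by a maximum observable window of 8 weeks from the dose of bezlotoxumab".

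**Relapse definition.** Section 2.5 (Definitions) requires onset more than 48 hours after antibiotic exposure and, in item 2, "Occurring within 8 weeks of completion of the high risk antibiotic course". Where signs were already present at antibiotic onset or within 48 hours, item 3 says "this was deemed a recurrence of infection NOT attributable to the high risk antibiotic course and was omitted from the relapse population".

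**Follow-up.** Sections 2.3 and 2.5 give 8 weeks of chart review, which section 2.5 counts from enrolment. Current diarrhea that may be due to CDI excludes a patient at enrolment.

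**Controls.** Section 2.3 names the institution's earlier retrospective study as a comparator and says the design was chosen "to allow comparisons with the historical treatment groups in that study". Section 2.7 makes that group one of three no-prophylaxis subgroups in the per-protocol population, which section 2.3 makes the primary analysis. The Power/Sample Size text takes the 26.7% planning rate from it (23 of 86 aged 60 or over). It also lets the concurrent controls be supplemented by retrospective charts analysed as in the prospective study, or by merging with the historical control arm.

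**The concern.** A bezlotoxumab patient has a dosing date and a concurrent decliner has a refusal date. A historical control or a retrospective-chart control has neither, because nobody offered them the study. The readable text assigns no substitute. The one relapse window that can be applied to such a patient as written is the course-based window in section 2.5, and that is not the window of the primary endpoint.

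Two differences follow if it is used. The window can stay open longer than 56 days after a comparable entry date. It can also count relapses that happened before such a date, whereas a prospective patient with diarrhea that might be CDI could not have entered. A merged or side-by-side comparison would then combine a difference in time at risk with any drug effect. The historical group also supplies the rate on which the sample sizes rest.

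**Working it through.** **1. How far the plan leans on the historical rate.** Inputs from Power/Sample Size: control 26.7%, bezlotoxumab 12.2% or 15.2%, two-sided alpha 0.05, power 80%. Treating 26.7% as a known constant,

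n = [1.960·√(p0(1−p0)) + 0.842·√(p1(1−p1))]² / (p0−p1)²

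- p1 = 0.122: (0.867 + 0.275)² / 0.145² = 62.1 (plan: 62)
- p1 = 0.152: (0.867 + 0.302)² / 0.115² = 103.4 (plan: 103)

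Both figures reproduce. An equal-allocation two-sample formula gives 116 and 196 per arm, which does not match. The stated sizes therefore rest on 23/86 directly, and the readable text does not state its window.

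**2. The two windows on one axis.** Measure days from entry, or from a comparable date in a control chart. Let S be the days from course start to that date, and E the days from that date to course end (negative if the course ended first). Exposure is read as starting with the course.

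| Rule | Opens | Closes |
|---|---|---|
| Primary endpoint (2.7) | day 0, no diarrhea possibly due to CDI | day 56 |
| Course-based definition (2.5) | day 2 − S | day 56 + E |

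The course-based window opens before entry whenever S exceeds 2, and the entry criteria put no limit on how long a course has already run. It closes after day 56 whenever the course ends after entry. High-risk antibiotic use must fall within 72 hours of enrolment, so E can be as low as about −3, and the window then closes near day 53. The plan gives no distribution for S or E, so no expected difference can be calculated.

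**3. Sensitivity to re-dating, as an example.** One historical relapse is 1/86 = 1.2 percentage points. The plan expects 50 bezlotoxumab patients; 6/50 (12.0%) is the count nearest to 12.2%. Two-sided p-values:

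| Historical relapses | Rate | Chi-square (uncorrected) | Fisher |
|---|---|---|---|
| 24/86 | 27.9% | 0.031 | 0.034 |
| 23/86 | 26.7% | 0.043 | 0.051 |
| 22/86 | 25.6% | 0.059 | 0.078 |

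At this count, moving one relapse changes the p<0.05 call: downward for chi-square, upward for Fisher. Other counts behave differently over 20 to 24 historical relapses:

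- 4/50 is significant throughout (chi-square 0.006 to 0.024).
- 5/50 needs three relapses to move (chi-square 0.039 at 21, 0.054 at 20).
- 7/50 (0.062 to 0.19) and 8/50 (0.11 to 0.31) are never significant.

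If the historical group is merged with an assumed 13/50 concurrent relapses, 6/50 gives chi-square p of 0.036, 0.045 and 0.056 against 36, 35 and 34 of 136, so two relapses must move.

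**The case against.** **How 23/86 was counted lies in a source we cannot see.** This stands. The historical survival analysis, "demonstrating the benefits of antibiotic prophylaxis on preventing relapsed CDI, is summarized in the following figure", is not shown in our text, and that figure may give its time origin. However, a retrospective study's origin cannot be bezlotoxumab dosing or refusal, so a mapping rule is needed whatever the figure shows.

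**Section 2.5 might look like proof that the historical count used the course-completion window.** A reader might infer this because item 3 is in the past tense, and because the prophylaxis rule ("prophylaxis used for at least 50% of the duration of the concomitant antibiotics course", plus the 72-hour condition) is the one section 2.3 attributes to the earlier study. That is an indication only. Item 2, which holds the limit, has no past-tense verb, and no passage says it produced 23/86.

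**The plan says retrospective charts get the prospective analysis.** This partly answers the point for those charts, since the entry criteria can be read from a chart. It still names no day 0 for a patient with no refusal date, and it does not cover the historical group.

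**The prospective arms might seem to have two contradictory endpoints.** The text does not support that. The two 8-week limits can be applied jointly, the entry limit binds whenever the course ends after entry, and section 2.5 treats the drug effect as lasting the whole 8-week observation period whatever the timing of antibiotic courses. The missing reference to refusal in the survival cap is clerical.

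**The p-values show ordinary small-sample fragility.** This is largely right. They show what one relapse is worth at one count and are not evidence that the windows differ.

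**Conclusion.** The point holds for the historical group and, to a lesser degree, for retrospective-chart controls. Their day 0 is undefined, and the only window the written rules can give them is not the primary endpoint's window. It should be settled before any control data are pooled, because choosing an index date after outcomes are known is an analyst choice that could alter the result.

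Size and net sign are unknown. A reader might conclude that the bias favours bezlotoxumab. A longer control window would push that way, but section 2.7 says less relapse information was available in the earlier study because outpatient records were not yet electronic, which could offset it. If 23/86 was already counted from a comparable entry date over 56 days, there is no mismatch. For scale, the exact 95% interval on 23/86 is 17.8% to 37.4%, so sampling error in that rate is wide in any case. Nor does this show that 62 and 103 are wrong for this reason; no corrected sizes follow from the documents.

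The comparison with concurrent decliners is not affected.

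**What to change.** 1. Give each historical and retrospective-chart control an index date: the first date on which the chart meets the entry criteria and the patient is relapse-free. Count relapses over 56 days from that date, as in the prospective arms.
2. State how 23/86 was counted. If those records cannot be re-dated, do not merge that group; report its comparison as secondary, with the concurrent decliners as the main comparator.
3. As a minor clarification, say that the limit of 8 weeks from entry governs the primary endpoint in the prospective arms, with items 1 to 3 of the section 2.5 relapse definition kept as attribution criteria. Add study refusal to the survival cap, which now refers only to the dose.

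The cost is a few sentences of protocol text and a limited re-review of up to 86 charts, if they can be retrieved (the documents do not say). If they cannot, the historical comparison becomes secondary and the main comparison loses precision.

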Procedures	
This prospective cohort study will be conducted using inpatients at the 1044 adult medical/surgical-beds on 2 campuses of the Montefiore Medical Center in the Bronx, New York. No work on this study will proceed until it is approved by our local Institutional Review Board.
 
SUBJECT IDENTIFICATION –INCLUSION CRITERIA
 
All patients with a laboratory diagnosis of CDI initially diagnosed within 3 months of screening, who are getting an order placed for inpatient antibiotics will be identified by bioinformatics—and will be eligible for study entry. They will be screened for concurrent use of metronidazole, oral vancomycin or fidaxomicin –if present; they will be rescreened for inclusion if further antibiotics are given without concurrent prophylaxis. If no prophylaxis is identified, then their providers will be approached to consider enrolling the patient into the current active arm for open-label Bezlotoxumab.
 
Inclusion criteria are :
 
 1. CDI within 90 days 2. Use of high-risk antibiotics for inducing CDI within 72 hrs of enrolment 3. No use of CDI active antibiotics within 24 hrs 4. Able to sign consent for the study, or have an identified surrogate. 
EXCLUSION CRITERIA
 
As this is a pragmatic study, reflecting mostly standard medical care, there are few exclusion criteria :
 
 1. Prior CDI episode was felt to be colonization after chart review(any physician-identified diarrhea is allowed, but not testing of asymptomatic patients such as test-of-cure testing or admission screening); 2. Subject not expected to survive 8 weeks; 3. Documentation of current diarrhea (3 or more unformed stools per day) at time of enrollment, possibly due to CDI. 4. Receipt of prior fecal microbiota transplant since the last CDI episode, or planned at time of screening or prior bezlotoxumab. 5. Congestive heart failure, as this diagnosis demonstrated increased mortality in the MODIFY studies with bezlotoxumab vs. placebo (Zinplava Package insert). 
CLINICAL DATA COLLECTION
 
Data on included patients will be collected by medical record review both manually and by using Clinical Looking Glass (CLG) software. Clinical data collected consists of patient demographics, comorbidities by ICD10 codes, length of hospital stay, nursing home residence, all antimicrobial agents received, use of proton pump inhibitors or histamine-2 blockers, all prior C. difficile assays, and severity of CDI markers on the date of CDI diagnosis – maximum temperature, maximum WBC, maximum creatinine, serum albumin –in order to calculate a Zar severity score (Zar, 2007). Manual chart reviews will be performed of all antibiotic courses for 8 weeks from enrollment and to assess for signs of CDI relapse, including symptoms such as abdominal pain or diarrhea as well as physical findings, vital signs, white blood cell, microbiologic data including both positive and negative C. difficile assays, and radiographic data. Particular weight will be given to assessment by infectious disease specialists, if consultation is performed.
 
DEFINITIONS
 
A valid high risk antibiotic course is defined as:
 
 1. Consisting of a beta lactam, carbapenem, quinolone, clindamycin, macrolide, or polymyxin, AND 2. Starting as early as 14days after the index CDI date, avoiding courses that

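### All-cause mortality and hospital stay are led by a per-protocol population defined by prophylaxis after entry, which biases the mortality ratio whenever exclusion differs between groups

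*Combined protocol and SAP*

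**What the plan says.** - **Population.** Section 2.7 (Statistical Methods): "The analysis population is the per-protocol population, with 2 major comparator groups", namely bezlotoxumab and no prophylaxis. Section 2.3 confirms the status of this population: "Patients receiving any such prophylaxis will be excluded from the per-protocol analysis, which will be the primary analysis".
- **Outcomes.** Section 2.7 lists among the secondary outcomes "all-cause mortality, time to relapse and duration of hospitalization". No outcome is given a different population. A later sentence says that pre-specified risk factors will be "tested for associations for the major outcomes of CDI relapse and mortality at 4 weeks and 8 weeks". That sentence is about risk factors rather than the drug comparison, but it shows that mortality is treated as a major outcome.
- **Exclusion rule.** The standard in Section 2.3 is "prophylaxis used for at least 50% of the duration of the concomitant antibiotics course", continued to within 72 hours of the end of that course. The rule is not limited to one group. The concurrent control arm is itself defined in Section 2.3 by taking no prophylaxis under the same definition.
- **Intent-to-treat.** Section 2.3: "Secondary analysis will also be performed on an intent-to-treat basis", with groups set by prophylaxis status at entry. Section 2.5 sends CDI-active drugs given after dosing to the same place: "potentially used within the Bezlotoxumab therapeutic window, will also be considered in secondary analyses (intent-to-treat").
- **Why deaths matter here.** Section 2.5 lists as an exclusion "Congestive heart failure, as this diagnosis demonstrated increased mortality in the MODIFY studies with bezlotoxumab vs. placebo".
- **Data.** Under Section 2.3, chart review every two weeks for 8 weeks covers the whole cohort and records relapse, tolerability, hospital and ICU stay, and death.

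**The concern.** Whether a patient later receives oral or intravenous CDI-active drugs has no bearing on whether that patient was exposed to the infusion. Yet it decides whether the patient counts in the lead mortality comparison. A patient who dies before prophylaxis starts cannot be excluded. A patient who lives long enough to receive a qualifying course is excluded, whether he or she then survives or dies. The people removed are therefore selected on having survived for a time, and the death rate among those left is too high in any group to which the rule is applied.

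If both groups lose the same share at the same time, both rates are inflated but the ratio is intact. If the shares differ, the ratio is biased. In an open-label study with decliners as controls there is no reason to expect equal shares. The protocol excludes heart failure because of a mortality signal with this drug, so a mortality comparison that can be shifted in either direction by later prescribing is a poor lead analysis.

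**Working it through.** **Inputs from the documents.** About 50 patients per concurrent group (Sections 2.6 and 2.7), 8 weeks of follow-up, and the exclusion rule above. There is no plan figure to reproduce: the documents state no mortality rate, no rate of prophylaxis after entry and no sample size for mortality. The stated sizes of 62 and 103 concern relapse and do not enter here.

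**Assumed inputs.** True 8-week mortality *m* is the same in both groups, at 10%, 15% or 20%. The hazard is constant. A share *q* of patients alive at week *t* (1, 2 or 4) is dropped. The dropped patients have the same later hazard as everyone else.

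**Formulas.**
- Weekly hazard λ = −ln(1 − m)/8
- Alive at week t: S = exp(−λt)
- Dropped: d = qS
- Later death risk of those dropped: r = 1 − exp(−λ(8 − t))
- Per-protocol mortality = (m − d·r)/(1 − d)

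**Worked case, m = 15%, t = 2.** λ = 0.1625/8 = 0.0203, S = 0.960, r = 0.115.
- q = 10%: d = 0.096, mortality = (0.150 − 0.011)/(1 − 0.096) = 15.4%.
- q = 30%: d = 0.288, mortality = (0.150 − 0.033)/(1 − 0.288) = 16.4%.
- 10% of dosed patients and 30% of controls dropped: ratio 0.94. Reversed: 1.07.
- 20% dropped in both: 15.8% against 15.8%, ratio 1.00.

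**Grid of ratios (dosed/control), true ratio 1.00.**

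| m | t (weeks) | drop 10% dosed, 30% control | drop 30% dosed, 10% control |
|---|---|---|---|
| 10% | 1 / 2 / 4 | 0.965 / 0.933 / 0.880 | 1.037 / 1.071 / 1.136 |
| 15% | 1 / 2 / 4 | 0.966 / 0.936 / 0.886 | 1.035 / 1.068 / 1.128 |
| 20% | 1 / 2 / 4 | 0.967 / 0.939 / 0.892 | 1.034 / 1.065 / 1.121 |

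The range is 0.88-0.97 in one direction and 1.03-1.14 in the other.

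**Extreme case.** Suppose no dropped patient dies. With 50 per group, 5 deaths in each, and 5 dosed patients and 15 controls dropped, the rates are 5/45 = 11.1% and 5/35 = 14.3%, ratio 0.78. Reversed, the ratio is 1.29.

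**Does the intent-to-treat analysis remove the problem?** Keeping everyone in the group held at entry returns 1.00 under these assumptions. But the stated grouping variable is prophylaxis at entry, and prophylaxis is defined as metronidazole, oral vancomycin or fidaxomicin. Inclusion criterion 3 (Sections 2.3 and 2.5) requires no CDI-active antibiotic in the preceding 24 hours. Dosed patients and otherwise eligible decliners are therefore both without prophylaxis at entry, and the variable does not literally tell them apart.

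**The case against.** The strongest reply is that the plan already has an analysis that keeps these patients. The intent-to-treat analysis is not limited to relapse. Section 2.5 routes later CDI-active drugs to it, which makes sense only if dosed patients stay in. Section 2.7 names the groups as bezlotoxumab and no prophylaxis, so a sensible analyst would probably group by the infusion. This largely stands: it would be wrong to say that the plan has no such analysis. What remains is that it ranks second for mortality and that its written grouping rule needs repair.

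A reader might infer that dosed patients who die disappear from the safety record. The documents do not support that. Under Section 2.9 serious adverse events are tabulated, deaths within 30 days potentially ascribed to the drug are reported, and a Safety Officer reviews all serious events after 12 and 25 subjects. None of this is limited to per-protocol. However, Section 2.9 specifies no comparison between groups, and its scheduled health queries cover active subjects only.

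It is also fair to say that the bias is small beside the sampling error. Take 15% mortality, 50 per group, and no deaths among the dropped, with 10% of dosed survivors and 30% of control survivors removed. That leaves 7.5 expected deaths among 45.75 and 37.25 patients, a ratio of 0.164/0.201 = 0.81. The standard error of its logarithm is √(1/7.5 − 1/45.75 + 1/7.5 − 1/37.25) = 0.467, so the approximate 95% interval is 0.33 to 2.03. This stands, and with the pilot status it limits the weight of the point. It does not justify keeping an avoidable bias when the data to avoid it are already collected.

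**Conclusion.** The point holds, as a change that should be made. As written, the lead comparison for mortality and hospital stay depends on an event after entry that patients must survive to have. Mortality is inflated within each group affected, and the ratio is biased when exclusion differs by group: about 0.88-0.97 with 10% of dosed patients and 30% of controls dropped, 1.00 with equal dropping, about 1.03-1.14 with the shares reversed, and further from 1 if nobody dropped dies. These figures rest on assumed mortality, exclusion shares and timing. No size was worked out for hospital stay.

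A reader might infer that the rule makes bezlotoxumab look protective or hides a harm. That requires more dropping among controls. It is plausible in an open-label study, and prophylaxis is common at this centre: about 50 of 150 eligible patients are expected to be on it (Section 2.6), and 104 of 248 (42%) received it in the centre's retrospective study (Section 2.7). But these are not rates of prophylaxis after entry by group, and the documents give none, so the direction is open. Nor is a much larger bias supported as the expected case. It requires that no excluded patient dies, whereas a patient who dies on a qualifying course can be excluded too, and covering half of the entry course implies starting soon after entry.

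The change below removes this selection only. Confounding from self-selected decliners remains.

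**What to change.** Add to Section 2.7: All-cause mortality and hospital and ICU stay are analysed primarily in all patients who received bezlotoxumab and all eligible concurrent decliners not on CDI prophylaxis at entry, grouped by receipt of the infusion, regardless of later CDI-active drugs; tolerability is reported in all patients who received the infusion.

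Alongside it:
- Report the per-protocol result for mortality and stay as a sensitivity analysis, with the number excluded and the number of deaths among them in each group.
- Show the historical controls separately for these outcomes. Their prophylaxis status was judged over the whole antibiotic course, so they may carry the same selection.
- Reword the intent-to-treat grouping in Section 2.3 so that it names receipt of the infusion.
- Keep per-protocol as planned for relapse.

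The cost is one sentence of analysis wording, a small clarification in Section 2.3 and one extra table. No new data are needed, because the two-weekly chart review already covers all cohort members.
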